8.4.7 MONTH 12 WASHOUT VISIT (DAYS 330 TO 420)

The Month 12 Washout visit is only intended for subjects presenting at the Month 12 visit on ocular hypotensive medication. This visit is conducted on the completion of medication washout for the purpose of obtaining an unmedicated IOP.

8.5 UNSCHEDULED VISITS

An unscheduled visit will be any visit to the clinical site, other than those specified in the protocol, at which the subject has a complaint regarding the study eye and/or treatment to the study eye is required or changed. The Investigator and/or qualified investigational staff will perform the procedures necessary to evaluate the study participant at these visits and will record the visit in the subject's medical records and on the CRF. No specific testing is required.

8.6 POSTOPERATIVE OCULAR HYPOTENSIVE MEDICATIONS

In general, the primary consideration for the reintroduction of hypotensive medication is the preservation of the retinal nerve fiber layer, optic nerve and visual field. Ocular

hypotensive medication “rescue therapy” will be introduced 1 month postoperatively or later to any subject if his/her IOP increases to > 21 mmHg at two consecutive visits within a two-week period. Administration of glaucoma medication in subjects with IOP < 21 mmHg will be considered on a case-by-case basis by the study Investigator and the Medical Monitor.

Re-introduction of hypotensive medications will be standardized as follows:

- The same medication class(es) as used preoperatively will be re-introduced
- Only one medication class may be reintroduced at any single visit.

Dependent on preoperative IOP medication use, the reintroduction/addition of IOP medications postoperatively should follow the order below:

1. Prostaglandin Analogues
2. Alpha Agonists
3. Beta Blockers
4. Carbonic Anhydrase Inhibitors (CAIs).

No more than one ocular hypotensive agent should be added at a single visit or within a 2-week period, without prior approval of the Medical Monitor.

8.7 SECONDARY SURGICAL INTERVENTIONS TO CONTROL IOP

If the subject requires another glaucoma procedure (surgical or laser) to control their IOP, the subject should continue to be followed according to standard of care until the AE that required the surgical treatment resolves or 1-month post-re-intervention, whichever is longer. Following this, the subject should be withdrawn from the study.

Subjects who have a secondary IOP-lowering intervention will be considered treatment failures for the purpose of the effectiveness evaluation. For the primary effectiveness endpoint of the study, the corresponding baseline unmedicated DIOP will be used to impute the 12-month unmedicated DIOP. These subjects will be included in the Safety Endpoint analyses through their withdrawal from the study.

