2 STUDY OBJECTIVE

First, to compare safety and effectiveness outcomes for canaloplasty and trabeculotomy using the OMNI Surgical System to implantation of the iStent inject in lowering intraocular pressure (IOP) in pseudophakic eyes with open angle glaucoma (OAG), and second, to compare safety and effectiveness outcomes for canaloplasty alone (using the OMNI Surgical System) to implantation of the iStent Inject in lowering intraocular pressure (IOP) in pseudophakic eyes with open angle glaucoma (OAG).

Objective 1:

The first objective is to evaluate, if for pseudophakic eyes with OAG, OMNI (canaloplasty AND trabeculotomy), is superior in lowering IOP to iStent inject.

Mean change in **unmedicated** DIOP from baseline at the 12-month postoperative examination will be used as a primary effectiveness endpoint to evaluate superiority of OMNI (canaloplasty AND trabeculotomy) compared to iStent inject in lowering IOP in pseudophakic eyes with OAG.

Objective 2:

The second objective is to evaluate if canaloplasty alone is non-inferior in lowering IOP (with a non-inferiority margin of 1.5 mmHg for comparing mean unmedicated diurnal IOP reduction at 12 months postoperative) to the iStent inject.

Mean change in **unmedicated** DIOP from baseline at the 12-month postoperative examination will be used as a primary effectiveness endpoint to evaluate non-inferiority of OMNI canaloplasty compared to iStent inject in lowering IOP in pseudophakic eyes with OAG.

The hypothesis is that the combined canaloplasty + trabeculotomy will be superior to iStent Inject and canaloplasty alone will be non-inferior to iStent Inject in lowering the IOP. Unmedicated diurnal IOP will be used to measure the change in the IOP as the primary effectiveness endpoint. The statistical approach is described in detail in Section 10 of this protocol. Diurnal IOP takes into consideration the fluctuations in IOP throughout the day and medication washout allows for isolating the effect of study treatments (1. Canaloplasty + Trabeculotomy, 2. Canaloplasty alone and 3. Trabecular bypass shunt i.e. iStent inject).

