10 STATISTICAL CONSIDERATIONS

10.1 SAMPLE SIZE OF THE STUDY

The sample size calculation is based on the primary effectiveness endpoint, mean change in unmedicated DIOP from baseline at the 12-month postoperative examination. The study goal is to determine, in reducing the IOP in the pseudophakic eyes with OAG, either OMNI (canaloplasty AND trabeculotomy) is superior to the iStent inject, or OMNI

(canaloplasty alone) is not inferior to the iStent inject in lowering the IOP with a non-inferiority margin of 1.5 mmHg. Due to the multiplicity, the significance level is adjusted to a two-sided significance level of 0.025 for each of the two hypotheses. The statistical hypotheses for the primary effectiveness endpoint are as follows:

A large black rectangular redaction box covers the majority of the page content, from approximately [113, 113] to [886, 300]. It is positioned in the center of the page, leaving a white margin on all four sides.

A large black rectangular redaction box covers the central portion of the page, obscuring several lines of text. On the far left edge of this redacted area, there are four small white vertical marks, possibly indicating where the text was originally aligned.

— 1 —

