10.4.2 SENSITIVITY ANALYSIS

A tipping-point analysis will be performed for the primary effectiveness endpoint. Let n and m be the number of OMNI and iStent inject subjects that do not have the 12-month washed out DIOP due to any reasons other than the first four criteria listed in Section

[10.4.1.](#) [REDACTED]

[REDACTED]

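### Section 8.7 scores every re-intervened eye as exactly zero change, which caps a failure's loss on the endpoint of the 1.5 mmHg non-inferiority test; a sensitivity analysis should vary that value

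*Combined protocol and SAP*

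**What the plan says.** Section 8.7 has three parts that matter here. It gives the label: "Subjects who have a secondary IOP-lowering intervention will be considered treatment failures for the purpose of the effectiveness evaluation". It gives the value for the primary endpoint: "the corresponding baseline unmedicated DIOP will be used to impute the 12-month unmedicated DIOP". And once the event has been followed up, it ends participation: "Following this, the subject should be withdrawn from the study". The section sets no condition on the pressure reached before the procedure.

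The same endpoint serves Objective 2. Section 2 says that mean change in unmedicated DIOP "will be used as a primary effectiveness endpoint to evaluate non-inferiority of OMNI canaloplasty compared to iStent inject", "with a non-inferiority margin of 1.5 mmHg for comparing mean unmedicated diurnal IOP reduction at 12 months postoperative". Section 10.1 states that "the significance level is adjusted to a two-sided significance level of 0.025 for each of the two hypotheses".

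The readable part of section 10.4.2 limits the tipping-point analysis to subjects who "do not have the 12-month washed out DIOP due to any reasons other than the first four criteria" of section 10.4.1. The list of criteria in 10.4.1, the rest of 10.4.2 and the body of 10.4.5 are redacted.

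**The concern.** The label and the value do not fit together for one kind of eye. An eye that is 3 mmHg above baseline and is not re-operated contributes +3. An eye with the same rise that is re-operated contributes 0. The declared failure then scores better than the eye that was left alone.

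This matters most for a non-inferiority claim. If canaloplasty is truly 1.5 mmHg worse, and eyes are re-operated because their pressure is high, that arm would have more capped eyes and larger losses capped. Part of the deficit would then drop out of the comparison. Treatment is unmasked after randomisation (section 5.2) and the readable text of 8.7 gives no criterion for re-intervention, so it is worth knowing whether the conclusion depends on this constant.

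**Working it through.** **1. The plan's own figures.** Completers are 137 per group with 10% drop-out (synopsis, section 5.1): 137/0.9 = 152.2, rounded up to 153, and 3 × 153 = 459. This reproduces. A two-sided level of 0.025 puts 0.0125 in the non-inferiority tail, z = 2.241. The 137 cannot be reproduced because SD and power are not readable. Solving SD = 1.5 / [(2.241 + z_power) × √(2/137)] with a true difference of zero gives 4.03 mmHg at 80% power and 3.52 at 90%. SDs of 3 to 5 are therefore assumed.

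**2. What decides the direction.** Let p be the re-intervention rate and x the change that those eyes would really have had (positive is worse), for canaloplasty (C) and iStent inject (I). Imputing zero moves the difference in favour of canaloplasty by

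shift = pC·xC − pI·xI.

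At a true deficit of 1.5, the false non-inferiority rate is about Φ(−2.241 + shift/SE), with SE = SD·√(2/137), which is 0.423, 0.483 and 0.604 for SD 3.5, 4 and 5.

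- Equal rates and equal x: shift 0, rate 1.25%.
- 10% v 5% (C v I), x = +4: shift 0.20, rate 2.8% (SD 5) to 3.9% (SD 3.5).
- 10% v 5%, x = −3: shift −0.15, rate about 0.5-0.6%.
- 5% v 10%, x = +4: shift −0.20, rate about 0.3-0.5%.

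**3. Re-intervention driven by pressure.** Assume a normal latent change, canaloplasty 1.5 mmHg worse, n = 137 per arm, and re-intervention in a share q of eyes with latent change above zero. With m the arm's mean change, the mean loss capped in an arm is g(m) = q·[m·Φ(m/SD) + SD·φ(m/SD)]. The hidden deficit is g(canaloplasty) − g(iStent inject). For iStent mean −5, SD 4, q = 0.5: 0.210 − 0.101 = 0.109 mmHg, or 7.3% of 1.5. False non-inferiority rates are from 20,000 simulated trials per row (simulation error about 0.1 to 0.15 points).

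| iStent mean | SD | q | Re-intervened, I / C | Hidden, mmHg (% of 1.5) | False non-inferiority |
|---|---|---|---|---|---|
| −7 | 4 | 0.5 | 2.0% / 4.2% | 0.045 (3.0%) | 1.7% |
| −7 | 4 | 1 | 4.0% / 8.5% | 0.090 (6.0%) | 2.1% |
| −7 | 5 | 0.5 | 4.0% / 6.8% | 0.080 (5.3%) | 1.8% |
| −7 | 5 | 1 | 8.1% / 13.6% | 0.160 (10.7%) | 2.6% |
| −5 | 4 | 0.5 | 5.3% / 9.5% | 0.109 (7.3%) | 2.4% |
| −5 | 4 | 1 | 10.6% / 19.1% | 0.218 (14.5%) | 4.5% |
| −5 | 5 | 0.5 | 7.9% / 12.1% | 0.149 (9.9%) | 2.5% |
| −5 | 5 | 1 | 15.9% / 24.2% | 0.298 (19.9%) | 5.2% |

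With the true values in place of zeros, the rate is 1.2-1.4% throughout.

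**4. Relaxing the trigger.** If 20-30% of eyes with latent change above −2, −3 or −4 mmHg are re-intervened, with the same means and SDs, some capped eyes are really below baseline. The rate is then about 1.0-2.0%, on either side of 1.25%.

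**5. Failure unrelated to response.** With the same failure share f in both arms and means −5.5 and −7 otherwise, the deficit becomes (1 − f) × 1.5: 1.425 at 5% and 1.35 at 10%. The per-arm variance is (1 − f)·SD² + f(1 − f)·m². For SD 5 down to 3, the rate is 1.7-2.0% at f = 5% and 2.3-3.0% at f = 10%.

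**6. What the proposed analyses recover.** In step 3, taking the worse of baseline and an accurate last value returns the rate to about 1.2-1.4%. If the last reading is lowered 2 mmHg by medication, it is about 1.5-2.8%. In step 5 the worse-of rule does almost nothing, because nearly all those eyes are below baseline. Setting canaloplasty failures 1.5 mmHg worse restores (1 − f) × 1.5 + f × 1.5 = 1.5.

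**The case against.** A reader might infer that the rule biases the trial towards a false non-inferiority claim. The documents do not support that. Baseline DIOP must be at least 22 mmHg (section 7.1), so it is selected to be high and regression to the mean works against later values above it. Rescue medication is tied to IOP above 21 mmHg (section 8.6), so an eye can be failing while still below its baseline; zero then takes credit away from it. Against an assumed mean change of −5 to −7, zero is a penalty. Steps 2 and 4 show neutral and conservative cases. This part of the objection stands.

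The largest rates in step 3 also sit badly with the plan. Re-intervened subjects are withdrawn, yet total drop-out is assumed to be 10%. The 4-5% rates need 19-24% re-intervention in the canaloplasty arm. This stands too. Step 5 can fairly be read as a choice of estimand, in which all failures count equally, rather than as an error.

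A reader might also infer that re-intervened eyes escape every sensitivity analysis. Section 8.7 gives them a fixed value and 10.4.2 sets four criteria aside, so it is probable that re-intervention is one of the four. But the list is redacted, and redacted text cannot be counted as absent.

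Finally, the last IOP before a procedure is an imperfect substitute. Unscheduled visits require no specific testing (section 8.5), and the reading may be single or medicated, whereas DIOP averages three. That argues against replacing the primary imputation. It does not argue against a sensitivity analysis.

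**Conclusion.** The point holds in a limited form. Section 8.7 caps a declared failure's loss at zero without condition, on the endpoint that carries the non-inferiority test. Whether this helps or hurts canaloplasty depends on the balance and severity of re-interventions, which the documents do not give.

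If re-intervention is concentrated in eyes above baseline and canaloplasty is truly 1.5 mmHg worse, the normal model of step 3 gives about 1.7-2.4% against 1.25% with at most 10% re-intervention in that arm, and about 4-5% only at 19-24%. The harsher fixed assumption in step 2, with every failing eye averaging 4 mmHg above baseline and a five-point excess in canaloplasty, gives 2.8-3.9%. Less selective re-intervention gives about 1.0-2.0%, and the opposite imbalance falls below nominal.

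All of this assumes SDs of 3 to 5 mmHg, the stated mean changes and re-intervention rates, and 137 analysed per arm. The stronger readings, that the rule favours a false claim or that the plan never varies the value, are not established. What is justified is a request to show that the non-inferiority conclusion does not rest on this constant. Confidence is medium.

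**What to change.** Keep the primary imputation. Unless redacted 10.4.1, 10.4.2 or 10.4.5 already does so, pre-specify for Objective 2 a sensitivity analysis with two parts:

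- (a) Impute each re-intervened eye with the worse (higher) of its baseline unmedicated DIOP and the last IOP available before the secondary procedure.
- (b) Extend the tipping-point analysis to these eyes, with separate shifts by arm, including the case where canaloplasty failures are set 1.5 mmHg worse than iStent inject failures.

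State that the non-inferiority conclusion should be shown to hold under both. If the redacted text already covers this, the sponsor need only confirm it.

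The cost is a few sentences and a little programming, with no new visits. The downside is that the result may look slightly less favourable. The last IOP may also be missing, single or medicated, so (a) can still understate some failures; (b) does not depend on that reading.

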8.8 WITHDRAWAL AND DISCONTINUATION

All subjects have the right to withdraw at any point during the study without prejudice. The Investigator can discontinue any subject at any time at his/her discretion, and must do so if continued participation in the study would result in harm to the subject. All efforts should be made by the Investigator to retain the subject in the study. If a subject withdraws prematurely from the study, a genuine effort must be made to determine the reason(s) the subject discontinued the study. The reason must be recorded in the subject's file and on the CRF.

8.9 SUBJECTS LOST TO FOLLOW-UP

Subjects who do not show up for a scheduled follow-up visit must be contacted to attempt to have them come for the visit. Every attempt at contacting the subject must be documented. If a subject misses two consecutive follow-up visits without any contact with the study staff, the subject will be considered lost-to-follow-up.

9 ADVERSE EVENTS (AE)

Adverse Events are defined below. AE that occurred in the study eye during the trial, whether they are considered to be device related or not, must be documented in the subject medical records and will be collected on the CRF. Date of the event, its severity, treatment (if any), and the assessed relationship of the event to the study device will be recorded on the Adverse Event Form (AEF). Conditions which existed prior to subject enrollment do not need to be recorded as AE unless they increase in severity or frequency during the study.

9.1 DEFINITIONS OF AE, SAE, SADE, USADE

Adverse Event	Any untoward medical occurrence in a subject who has been treated with the device that does not necessarily have causal relationship with the treatment.
Adverse Device Effect	Any unfavorable and unintended sign (including an abnormal laboratory finding), symptom, or disease that is possibly related to the study device.
Serious Adverse Event (SAE)	Any untoward medical occurrence that: 
• Results in death• Is life-threatening• Requires in-patient hospitalization or prolongs existing hospitalization• Necessitates medical or surgical intervention to preclude permanent impairment of a body function or permanent damage to a body structure• Sight threatening
Unanticipated Adverse Device Effect	Any serious adverse effect on health or safety, any life-threatening problem or death caused by, or associated with a device if that effect, problem, or death was not previously identified in nature, severity, or degree of incidence in the clinical investigational plan; or any other serious problem associated with a device that relates to the rights, safety, or welfare of subjects (21 CFR 812.3(s)). Any sight-threatening event, whether listed in the protocol or not, is considered to be reportable as a UADE

This figure is a 2D grayscale heatmap representing a complex, multi-peaked structure. The structure is highly concentrated in the center, with several distinct lobes extending towards the edges. The background is white, and the data is represented by varying shades of gray, with the highest intensity in the central region. The overall shape is roughly rectangular but with irregular, jagged edges, suggesting a noisy or high-resolution data set. The central peak is the most intense, with a smaller secondary peak visible on the right side.

9.3 REPORTING ADVERSE EVENTS

Identification, collection and reporting of AE information is the responsibility of the Investigator. The Investigator records the date of the event, its severity, treatment (if any) and the assessed relationship of the event to the study device on the AE CRF.

Any ocular-related **serious adverse event (SAE)** should be reported to study sponsor's clinical team within one business day of learning of the event. Non-ocular related SAEs should be reported to the study sponsor's clinical team within two working days of learning of the event. Email the AE CRF to [contact].

Any **unanticipated adverse device effects (UADE)** must be reported to the following two entities:

1. The study sponsor – Within one working day of the investigator first learning of the event, e-mail the AE CRF to [contact]; and
2. The responsible Ethics Committee – As soon as possible, but no later than 10 working days after the investigator first learns of the event, report per the EC's instructions.

The sponsor will conduct an evaluation of unanticipated adverse device effects. If the sponsor determines that an unanticipated adverse device effect presents an unreasonable risk to subjects, parts of the investigation presenting risks will be terminated. Termination will occur no later than 5 working days after the sponsor makes such a determination and no later than 15 working days after the sponsor first received notice of the effect.

10 STATISTICAL CONSIDERATIONS

10.1 SAMPLE SIZE OF THE STUDY

The sample size calculation is based on the primary effectiveness endpoint, mean change in unmedicated DIOP from baseline at the 12-month postoperative examination. The study goal is to determine, in reducing the IOP in the pseudophakic eyes with OAG, either OMNI (canaloplasty AND trabeculotomy) is superior to the iStent inject, or OMNI

(canaloplasty alone) is not inferior to the iStent inject in lowering the IOP with a non-inferiority margin of 1.5 mmHg. Due to the multiplicity, the significance level is adjusted to a two-sided significance level of 0.025 for each of the two hypotheses. The statistical hypotheses for the primary effectiveness endpoint are as follows:

A large black rectangular redaction box covers the majority of the page content, from approximately [113, 113] to [886, 300]. It is positioned in the center of the page, leaving a white margin on all four sides.

A large black rectangular redaction box covers the central portion of the page, obscuring several lines of text. On the far left edge of this redacted area, there are four small white vertical marks, possibly indicating where the text was originally aligned.

— 1 —

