5.1 NUMBER OF SUBJECTS, DURATION OF FOLLOW-UP AND STUDY DURATION

Approximately 459 subjects will be randomized (1:1:1) to treatment, approximately 153 in each group. This assumes a 10% drop-out rate over the 12-month follow-up period and ensures that 137 subjects per group will complete the 12 month study. No site will randomize more than 25% of the total number of subjects.

It is estimated that up to 40% of subjects will not meet IOP eligibility criteria following medication washout, or other inclusion/exclusion criteria failure preventing

randomization therefore up to 762 subjects may be enrolled in order to meet the targeted randomization of 459 subjects.

Study subject participation will be for approximately 12 months, 5 days (at a minimum) to 14 months, depending on the length of the required medication washout prior to baseline and if a terminal washout is needed (required for subjects presenting at the Month 12 visit and on ocular hypotensive medication).

It is anticipated that site initiation, subject recruitment and follow-up, and site close-out will require approximately 24 months.

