5.2 METHODS USED TO MINIMIZE BIAS

This study is randomized using block (a block of 6) randomization and neither the Investigator, the investigative site staff, or Sponsor clinical personnel will have knowledge of or access to the randomization scheme. Randomization to treatment group will be performed using a 1:1:1 ratio and will be stratified by site. Treatment allocation bias will thus be avoided. Once randomized into the study, the Investigator, the investigative site staff, Sponsor clinical personnel and the subject will be unmasked to the treatment assignment for each subject.

The study is multicenter with sites in at least 5 countries. The potential bias inherent in single-center trials is thus eliminated. Moreover, no site can randomize more than 25% of the study subjects. The location of sites in multiple countries incorporates greater diversity in the patient population as well as subtle geographic differences in treatment norms/standard of care allowing greater generalizability of the study results.

Mean diurnal IOP is the basis for the primary endpoint. DIOP averages three separate IOP measurements taken at different times of day. This mitigates the risk of a single measurement being unusually high or low and subsequent regression to the mean. IOP measurements will be taken using Goldmann applanation tonometry with routine and documented calibration required. IOP will be measured by 2 different study personnel (an operator and a recorder) closely following the procedure used in AGIS.¹⁹ This technique prevents unintentional bias on the part of the Investigator or technician measuring and recording the IOP.

Reintroduction and discontinuation of ocular hypotensive medications will follow a protocol defined procedure to ensure standardization across sites and remove the potential for bias in treatment regimen.

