10.6 INTERIM ANALYSIS

An interim analysis providing descriptive statistics for the outcomes may be completed following completion of the Month 6 follow-up visit by 80% of the randomized subjects. Endpoints listed below will be analyzed at an interim analysis. No device effectiveness will be claimed based on the interim analysis outcomes.

Effectiveness outcomes up to 6 months will be summarized descriptively:

1. Percent of eyes with a $\geq 20\%$ reduction in IOP with no increase in IOP-lowering medications compared to screening visit
2. Percent of eyes with IOP between 6 and 18 mmHg with no increase in IOP-lowering medications compared to screening visit
3. Percent of eyes with IOP between 6 and 21 mmHg with no increase in IOP-lowering medications compared to screening visit
4. Reduction in mean IOP from screening visit; and
5. Reduction in mean number of IOP-lowering medications from screening visit

Safety endpoints:

1. Rates of ocular adverse events (intraoperative, postoperative)
2. Reduction in BCDVA from screening (note: reduction in BCDVA due to worsening of PCO will not be treated as a safety event)
3. Secondary Ocular Surgical Interventions, including laser, for IOP control

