13 PROTOCOL MODIFICATIONS AND DEVIATIONS

Protocol modifications may occur during the study. Each will be approved in writing by the sponsor before implementation. Each will undergo Ethics Committee review and approval, as necessary.

Any deviations from this protocol intended to protect the life or physical well-being of a subject in an emergency are to be reported to Sight Sciences, Inc. as well as the Ethics Committee as soon as possible, and no later than 5 working days after the emergency occurred.

All protocol deviations will be documented using the Protocol Deviation form.

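### Two primary hypotheses at a fixed two-sided 0.025 each: valid, but unless the redacted text already steps down, Holm would raise the power of each claim, and of both together, with the same subjects

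*Combined protocol and SAP*

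**What the plan says.** Section 10.1 of the combined protocol and SAP sets the level for the two primary comparisons with iStent inject: "Due to the multiplicity, the significance level is adjusted to a two-sided significance level of 0.025 for each of the two hypotheses". No family-wise level is stated in the visible text; 2 x 0.025 implies two-sided 0.05.

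The two claims are worded in two ways. Section 10.1 gives the study goal as alternatives: "either OMNI (canaloplasty AND trabeculotomy) is superior to the iStent inject, or OMNI" (canaloplasty alone) is non-inferior with a margin of 1.5 mmHg. Section 2 numbers two objectives, the first on superiority of the combined procedure, and then: "The second objective is to evaluate if canaloplasty alone is non-inferior in lowering IOP". It goes on to state the study hypothesis with both claims joined by an 'and'.

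On size, Section 5.1 randomizes 459 subjects 1:1:1 and says that a 10% drop-out allowance "ensures that 137 subjects per group will complete the 12 month study".

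The visible text contains no step-down, fixed-sequence or alpha-recycling rule. The only other multiplicity method is Dunnett's test in Section 10.4.4, for analyses described as exploratory. The remainder of 10.1 and all of 10.4.1, where a testing procedure would normally stand, are redacted.

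**The concern.** With a fixed split, each claim must be won at 0.025 whatever happens to the other. Once one hypothesis has been rejected, only one null can still be true, and the full 0.05 can be spent on it without exceeding the family-wise level. The fixed split leaves that level unused. Holm uses it.

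What is at stake is the power of each separate claim and of winning both. That matters if the trial is judged as Section 2 words it, with two numbered objectives and a joint hypothesis. A trial could show superiority of the combined procedure, then miss non-inferiority of canaloplasty alone with a p-value between 0.025 and 0.05, and make no second claim although the error budget allowed it.

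**Working it through.** **Inputs from the document.** Two hypotheses at two-sided 0.025 each (10.1); a shared iStent inject arm and 1:1:1 allocation (Section 5); 137 completers per group and 10% drop-out (5.1).

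**The plan's own figures.** 137 / (1 - 0.10) = 152.2, rounded up to 153 per group; 3 x 153 = 459. This agrees with the plan. The implied family-wise level is 0.025 + 0.025 = 0.05. The 137 itself cannot be reproduced, because the SD, the superiority effect and the planned power are redacted.

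**Assumptions.** The test statistics Z1 and Z2 are bivariate normal. Their correlation is 0.5, which follows from a shared control with equal arm sizes and equal variances. Power at 0.025 is assumed, over a range.

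**Formulas.** The critical values are c1 = 2.241 (two-sided 0.025) and c2 = 1.960 (two-sided 0.05). For assumed power p, the mean of Z is c1 + z(p): 3.083 for 80%, since 2.241 + 0.842 = 3.083, and 3.523 for 90%.

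- Split: claim i is won if Zi > c1.
- Holm: claim i is won if Zi > c1, or if Zi > c2 and the other Z > c1.
- Holm power for claim i = P(Zi > c1) + P(Zi > c2, Zj > c1) - P(Z1 > c1, Z2 > c1).
- Both claims under Holm = P(Z1 > c2, Z2 > c1) + P(Z1 > c1, Z2 > c2) - P(Z1 > c1, Z2 > c1).
- At least one claim = P(Z1 > c1 or Z2 > c1), the same under either rule.

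**Worked case, 80/80.** P(both > c1) = 68.72%, and P(Z1 > c2, Z2 > c1) = 73.28%. Each claim under Holm: 80.00 + 73.28 - 68.72 = 84.56%. Both under Holm: 73.28 + 73.28 - 68.72 = 77.84%. At least one: 80 + 80 - 68.72 = 91.28% under both rules.

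| Power at 0.025 (claim A / claim B) | Holm, claim A | Holm, claim B | Both: split | Both: Holm | At least one (both rules) |
|---|---|---|---|---|---|
| 80% / 80% | 84.56% | 84.56% | 68.72% | 77.84% | 91.28% |
| 90% / 90% | 93.06% | 93.06% | 83.24% | 89.36% | 96.76% |
| 80% / 90% | 85.68% | 92.30% | 75.15% | 83.13% | 94.85% |
| 50% / 80% | 59.01% | 81.99% | 45.64% | 56.64% | 84.36% |
| 20% / 80% | 28.02% | 80.43% | 19.16% | 27.61% | 80.84% |

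A simulation of 4,000,000 pairs agreed for the first two rows (each 84.55% and 93.03%, both 77.84% and 89.32%). The correlation matters little: over 0.3 to 0.7, each claim at 80/80 reaches 84.97% to 84.07%, and at 90/90 93.34% to 92.70%. The balance of power between the claims matters more. In the last row the stronger claim gains only 0.4 points.

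**Error.** With both nulls true, the two-sided family-wise error is 0.0465 under either rule. With one null true it is at most 0.05 under Holm. In the favourable direction, the error for a single true null rises from 1.25% under the split to 2.48% (other claim at 80% power) or 2.50% (other at 90%).

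**Why a direction condition is needed.** Suppose one comparison is truly unfavourable (the mirror image of 80% or 90% power) and the other null is true. If a significant unfavourable result also released the 0.05 level, the favourable-direction error would be 1.76% or 2.01%. With the condition it stays at 1.25%.

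**The case against.** The strongest objection is that the visible plan may not be a fixed split at all. The quoted sentence stands in the sample-size section, and sizing each test at 0.025 is also what a Holm plan would do. A reader might infer that the plan lacks a step-down rule. The documents do not support that, because the places where it would be stated are redacted. This stands, and the point is therefore conditional.

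Second, a reader might infer that Holm makes the trial more likely to succeed. Under the goal as 10.1 words it, "either OMNI (canaloplasty AND trabeculotomy) is superior to the iStent inject" or the other claim holds, so success means at least one win, and that probability is identical under both rules. This also stands. The gain is per claim and for both claims, and its relevance comes from Section 2.

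Third, nothing visible suggests equal power for a superiority claim and a non-inferiority claim with a 1.5 mmHg margin, so the equal-power rows alone would flatter the change. For the same reason, the gain should not be restated as a number of subjects saved: with unequal power no single number fits both claims.

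Fourth, the split has merits. It gives one fixed 97.5% interval per claim and a stricter error for each claim. A sponsor may reasonably prefer that.

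Finally, feasibility is unknown. Section 5.2 says that after randomization the "Sponsor clinical personnel and the subject will be unmasked to the treatment assignment for each subject", and Section 10.6 says: "An interim analysis providing descriptive statistics for the outcomes may be completed following completion of the Month 6 follow-up visit". The documents do not show whether comparative data have been seen.

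**Conclusion.** The equal split is valid and somewhat conservative, and the plan contains no error here. Provided that neither 10.1 nor 10.4.1 already steps down, Holm is at least as powerful for every claim, whatever the correlation, and keeps the family-wise error within the implied two-sided 0.05. That ordering does not depend on the redacted quantities; the size of the gain does.

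Over the range examined, at correlation 0.5, the gain is 0.4 to 9.0 points for a single claim and 6.1 to 11.0 points for winning both. It is nil for at least one success. The point is optional, of low severity, and of value mainly if both objectives in Section 2 are to be claimed.

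**What to change.** First check the unredacted 10.1 and 10.4.1. If a step-down rule is already there, nothing needs to change. Otherwise, keep the sample size and add to the primary analysis:

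> The two primary hypotheses will be tested with the Holm procedure at family-wise two-sided 0.05: the smaller p-value at 0.025 and, if it is significant in the favourable direction (superiority shown, or non-inferiority to the 1.5 mmHg margin shown), the other at 0.05. If it is significant in the unfavourable direction, the other stays at 0.025. Either claim may be made without the other. The governing confidence interval is the 97.5% interval for a claim tested at 0.025 and the 95% interval for a claim tested at 0.05.

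Make the change by a dated amendment before any comparative outcome data are reviewed, including the optional interim summaries in 10.6. If comparative data have already been reviewed, keep the split.

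The cost is one amendment; on review, Section 13 says of protocol modifications: "Each will undergo Ethics Committee review and approval, as necessary". No extra subjects or visits are needed. There are two statistical costs. The favourable-direction error for a single true null rises from 1.25% to at most 2.5%. A claim won only at the second step is not matched by its 97.5% interval. Under the illustration this happens in 9.1% of trials at 80/80 (77.84 - 68.72) and 6.1% at 90/90 (89.36 - 83.24), which is why the governing interval has to be fixed in advance.
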